### **4.3 EXCLUSION CRITERIA**

- <18 years of age
- Takatsubo cardiomyopathy
- Myocarditis
- Renal failure (estimated glomerular filtration rate <30 mL/min/1.73 m^2)
- Woman of child-bearing potential who are pregnant or breastfeeding
- Known allergy or contraindication to iodinated contrast or radiotracer
- Patients unable to tolerate the supine position
- Patients unable to provide informed consent

### **4.4 CO-ENROLMENT**

Co-enrolment with other studies may be considered in line with ACCORD co-enrolment policy. Co-enrolment between studies will be agreed by the respective PIs prior to beginning of the study. Individual patients who are eligible for co-enrolment will be discussed between research fellows and PIs as necessary. This will ensure co-enrolment:

1. Is appropriate (i.e. there are no contra-indications)
2. Would not jeopardise the integrity of either study
3. Would not compromise patient care, safety, or result in an undue burden on the patient, including exposure to too much radiation.

## **5 PARTICIPANT SELECTION AND ENROLMENT**

### **5.1 IDENTIFYING PARTICIPANTS**

Potential participants for all the cohorts will be identified by their usual care team whilst in the Royal Infirmary of Edinburgh. A member of the study team will provide an information sheet if the participant is interested in taking part in the study.

### **5.2 CONSENTING PARTICIPANTS**

Participants will be enrolled following an opportunity to read the patient information sheet and once written informed consent is obtained, screening for eligibility can begin. Consent will be confirmed at the beginning of any study activities.

#### **5.2.1 Withdrawal of Study Participants**

Participants are free to withdraw from the study at any point or a participant can be withdrawn by the Investigator. If withdrawal occurs, the primary reason for withdrawal will be documented in the participant's case report form if possible. The participant will have the option of withdrawal from:

- (i) all aspects of the study but continued use of data collected up to that point. To safeguard rights, the minimum personally identifiable information possible will be collected.

## **6 STUDY ASSESSMENTS**

### **6.1 STUDY ASSESSMENTS**

All patient's eligible for the study will have informed consent taken. This will as well as a standardised clinical assessment will be performed either whilst still an inpatient or as soon as practical possible from symptom onset. The clinical assessment will be carried out in the Clinical Research Facility or on participants' inpatient ward.

### **6.2 Study Screening**

Eligible participants in will be approached as described in section 5. We will also assess capacity to ensure adequate understanding of the study procedures and their ability to provide informed written consent.

### **6.3 Baseline Visit**

All patient's eligible for the study will have informed consent taken. This will as well as a standardised clinical assessment will be performed either whilst still an inpatient or as soon as practical possible from symptom onset. The clinical assessment will be carried out in the Clinical Research Facility or on participants' inpatient ward.

The assessment will include:

- Demographic details
  - o Name, initials, age, sex, height, weight, CHI number, telephone number, address, postcode and email address if available
- Past medical and surgical history
- Medications
- Allergies
- Clinical examination
  - o Blood pressure assessment and heart rate
  - o Physical examination by clinically qualified study researcher including cardiovascular examination
- Electrocardiography (assessing for evidence of myocardial infarction and arrhythmia)
- Clinical haematology and biochemistry will be recorded as part of standard of care.
- A urinary pregnancy test in women of childbearing potential

### **6.4 Echocardiography**

Transthoracic echocardiography will be performed by a British Society of Echocardiography-accredited research ultra-sonographer according to American Society of Echocardiography and European Association of Cardiovascular Imaging guidelines. Patients will be studied with a standard 3 MHz transducer and 2- dimensional, M-mode, Doppler and colour Doppler measurements taken. Ejection fraction will be quantified using the modified Simpson's technique and regional wall motion abnormalities assessed. Agitated saline and ultrasound contrast will be performed to assess for intracardiac shunts and left ventricular thrombus as appropriate. If not performed as part of standard of care, we will organise a study specific

transthoracic echocardiogram to be performed at baseline visit or as soon as possible as when is convenient for the participant.

## **6.5 Invasive coronary angiography and intravascular imaging**

Invasive coronary angiography will be performed in all patients. Adjunctive imaging with optical coherence tomography (or intravascular ultrasound) will be encouraged as part of standard of care.

## **6.6 Cardiac magnetic resonance imaging**

All patients will undergo cardiac magnetic resonance imaging as standard of care for the investigation of patients with myocardial infarction and non-obstructive coronary arteries or myocardial infarction of uncertain aetiology. This will be performed prior to  $^{18}\text{F}$ -GP1 PET/CT coronary angiography to exclude patients without myocardial infarction, such as those with myocarditis or takotsubo cardiomyopathy.

## **6.7 Hybrid $^{18}\text{F}$ -GP1 positron emission tomography and coronary computed tomography coronary angiography**

$^{18}\text{F}$ -GP1 will be synthesized by our radiochemistry facility, the Edinburgh Imaging Facility Radiochemistry (EIFR), which is co-located within our Edinburgh Imaging Facility, Queens Medical Research Institute (EIF QMRI) using our well-established protocols. Each patient will undergo  $^{18}\text{F}$ -GP1 PET/CT coronary angiography imaging on our hybrid scanner (Biograph mCT, Siemens) as soon as practical after their index event and within a maximum of 7 days from symptom onset. In our previous studies the  $^{18}\text{F}$ -GP1 signal diminished after this time point (35). Patients will initially be injected with 250 MBq  $^{18}\text{F}$ -GP1, before resting in a quiet environment for 60 min. A low-dose attenuation correction CT scan (120 kV, 50 mAs, 5/3 mm) will be followed by acquisition of PET data in list mode using a two 20-min bed position centred on the thoracic aorta and heart. A contrast-enhanced CT coronary angiogram will then be performed. After optimal co-registration of the CT and PET data, regions of interest will be drawn for PET quantification around areas of uptake in the coronary arteries, ascending and arch of the aorta as well as the atria and ventricles of the heart. Mean and maximum standardised uptake values (SUV) for  $^{18}\text{F}$ -GP1 uptake will be measured. Tissue to background ratio (TBR) will also be calculated after correcting thrombus uptake for tracer activity in the blood pool of the right atrium as described previously (37).

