## **2.2 ENDPOINTS**

### **2.2.1 Primary Endpoint**

The primary endpoint will be the degree and location of platelet activation as determined by the target to background ratio of F-GP1.

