## **4 STUDY POPULATION**

### **4.1 NUMBER OF PARTICIPANTS**

We will recruit two patient populations after invasive coronary angiography has been completed. We have established comparator control populations including 50 patients with stable coronary artery disease (no angina or recent myocardial infarction) and valvular heart disease who underwent F-GP1 cardiac PET-CT as part of a concurrent study (NCT04073875) (34).

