## 9 STATISTICS AND DATA ANALYSIS

### 9.1 SAMPLE SIZE CALCULATION

We have found that  $^{18}\text{F}$ -GP1 is markedly discriminatory for the presence of thrombus with an accuracy of 96% with 100% specificity and false negatives predominantly seen in patients imaged beyond 7 days from presentation (37). The prevalence of coronary thrombosis in patients with myocardial infarction and non-obstructive coronary arteries is unknown but estimates suggest that plaque disruption may be as high as one third of cases although it is unclear if this is bystander disease or the cause of the infarction (19). We have estimated that routine clinical evaluation may suggest thrombus in 10-20% of patients with myocardial infarction and non-obstructive coronary arteries. For 80-90% power at two-sided  $p < 0.05$ , we will require a study population of 36-50 to detect an incidence of thrombosis of 25-40%. Population sizes for coronary thromboembolism and spontaneous coronary dissection are based on the proof-of-principle of the detection of coronary thrombosis and have greater than 95% power to detect a prevalence of coronary thrombus in over two thirds of patients.

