### 9.2 PROPOSED ANALYSES

As with our previous studies, image analysis will be performed on bespoke PET analysis software from our long-standing collaborators (FusionQuant, Cedars Sinai Hospital, Los Angeles) that provides automated motion correction and advanced cardiovascular PET quantification (31, 32, 38). After accurate co-registration of the PET and CT data sets,  $^{18}\text{F}$ -GP1 uptake will be quantified within regions of interest around areas of thrombus on the CT images.

Descriptive statistics will incorporate numbers and proportions, means and standard deviations or median and interquartile ranges. Proportions will be compared with Chi-squared test and continuous variables will be compared with regression analysis, Student's *t*-test or analysis of variance with repeated measures for longitudinal assessments. Statistical significance will be taken as two-sided  $p < 0.05$ .

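### Coronary TBR, the measure of degree in the primary endpoint, is defined only where uptake or thrombus is already seen, so it is conditional on positivity and has no sound comparison with controls

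*Protocol*

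**What the plan says.** - **Endpoint (Protocol 2.2.1).** The primary endpoint is the "degree and location of platelet activation as determined by the target to background ratio of" 18F-GP1. Presence of activation is a secondary endpoint (2.2.2).
- **Region rule in 6.7.** After co-registration, "regions of interest will be drawn for PET quantification around areas of uptake in the coronary arteries"; the same sentence goes on to the aorta and the cardiac chambers. TBR is then "calculated after correcting thrombus uptake for tracer activity in the blood pool of the right atrium".
- **Region rule in 9.2.** Here "uptake will be quantified within regions of interest around areas of thrombus on the CT images".
- **Comparator (4.1).** "We have established comparator control populations including 50 patients with stable coronary artery disease" and valvular heart disease, scanned in a concurrent study. Section 3 calls the design a case-control cohort study.
- **Expected yield (9.1).** Earlier work gave an "accuracy of 96% with 100% specificity". Cohort 1 is sized for a thrombosis incidence of 25-40%. Section 1.1.5 adds that uptake was seen only in culprit arteries of patients with acute infarction.
- **Tests (9.2).** Chi-squared for proportions; regression, t-test or analysis of variance for continuous variables.

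No section gives a region, or a value, for a coronary artery with neither uptake nor thrombus, and none gives a region rule for the control scans.

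**The concern.** Two rules are stated for the same measurement. One lets PET define the site and the other lets CT define it. They can disagree: a patient may have uptake with no thrombus visible on CT, or the reverse. Choosing one of them removes the contradiction but not the larger difficulty, which is that either rule yields a coronary TBR only once a site has been called positive.

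A variable measured only in positives answers a narrow question: how intense is the signal where there is one? It cannot describe the degree of coronary platelet activation across a cohort, and it has no natural counterpart in a control group expected to be negative. A patient with several foci would also contribute several values, with no rule for reducing them to one.

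At stake is the degree part of the primary endpoint in the coronary arteries, and its comparison with the 50 controls. This is not a detail left for an analysis plan. The measurement rule is written into the protocol and governs what readers record.

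**Working it through.** **1. The protocol's own figure.** Section 9.1 gives 36-50 patients for 80-90% power at two-sided 0.05. For a one-sample proportion, n = [(1.96·√(p0(1−p0)) + z·√(p1(1−p1))) / (p1−p0)]². Taking p0 = 0.20 and p1 = 0.40:

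- 80% power: [(1.96×0.400 + 0.842×0.490)/0.20]² = 35.8, so 36.
- 90% power: [(1.96×0.400 + 1.282×0.490)/0.20]² = 49.8, so 50.

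The stated range reproduces for 20% against 40%. (10% against 25% gives 41 and 59, so the low end fits less well.) The study is therefore sized on a proportion, and TBR plays no part in the sizing.

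**2. Cohort 1 patients with a coronary TBR.** Expected number = N × incidence × sensitivity, with N = 50 (4.1.1) and incidence 25-40% (9.1). The protocol gives no sensitivity. With 100% specificity, 96% accuracy implies sensitivity = 1 − 0.04/prevalence. That is 0.84 or 0.90 if the prevalence in the validation data was 25% or 40% (assumed).

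| Incidence | Sensitivity | With a value | Without |
|---|---|---|---|
| 25% | 1 | 12.5 | 37.5 (75%) |
| 25% | 0.84 | 10.5 | 39.5 (79%) |
| 40% | 1 | 20 | 30 (60%) |
| 40% | 0.90 | 18 | 32 (64%) |

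These counts apply to uptake-defined regions. The protocol gives no figure for how often thrombus is visible on CT, so the yield of the 9.2 rule cannot be calculated.

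**3. Controls.** Expected number = 50 × (1 − specificity). At 100% this is 0. At an assumed 95-99% it is 2.5 to 0.5. Both apply only if the earlier performance carries over to these scans.

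**4. What a positives-only mean can show.** Assume TBR 2.0 (SD 0.5) at positive sites and 1.0 (SD 0.2) elsewhere; these values are illustrative and are not in the protocol. The positives-only mean is 2.0 whatever the frequency p. The all-patient mean is 2.0p + 1.0(1−p), which is 1.10 at 10% and 1.40 at 40%.

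**5. Is a difference in frequency lost?** Under the same assumptions, 10% against 40% positive, 50 against 50, 4,000 simulated studies, share with p < 0.05:

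| Comparison | Share |
|---|---|
| Positives-only TBR, Welch t-test | 6-7% |
| All-patient TBR, Welch t-test | about 84% |
| Presence or absence, Chi-squared | 96% (93% with continuity correction) |

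Positives-only TBR rejects at close to the nominal 5%, since intensity among positives was set equal in the two groups. The presence comparison, which 2.2.2 and 9.2 already provide for, finds the frequency difference more often than all-patient TBR does.

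**The case against.** **Negatives are not declared missing.** The protocol nowhere says that negative patients or controls go unmeasured, or that a mean among positives will be reported. That is correct. The absence of a value is inferred from the two region rules and the lack of any other. An analysis plan can say how to treat a patient without a region, but it cannot supply a coronary measurement that readers were never told to make. The scans are kept, so the gap can be closed later; closing it before reading is cleaner.

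**The endpoint is not only coronary.** The region sentence in 6.7 also names the aorta, atria and ventricles, and 1.1.5 reports intramyocardial uptake and chamber thrombus. A patient without coronary uptake could still have a non-coronary TBR. This stands, and it confines the point to coronary TBR. A reader might infer that most of Cohort 1 has no primary-endpoint value at all; the text does not support that.

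**The control count is not established.** A reader might infer that exactly none of the 50 controls has a value and that the case-control contrast cannot be computed. The 100% specificity comes from earlier data, the controls include valve patients, and the protocol is silent on how their scans were or will be quantified. Few or none is a fair expectation, but it is not a documented fact.

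**Frequency plus intensity among positives is a coherent description.** It is, and it fits the objective in 2.1.1. A reader might infer that a real difference in frequency would be hidden; step 5 of the working shows that it would not. What this two-part description still lacks is a comparison of coronary degree with controls.

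**Conclusion.** The point holds for coronary TBR. Sections 6.7 and 9.2 give conflicting region rules, and both make the coronary part of the primary variable conditional on a positive finding. At the protocol's own incidence, about 12-20 of 50 Cohort 1 patients would have a value (down to about 10 if sensitivity is imperfect). If earlier specificity and culprit-only uptake carry over, few or none of the 50 controls would. The coronary degree result would then describe positives only, and a comparison with controls would not be meaningful.

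The Cohort 1 count assumes that the protocol is followed as written and that incidence is 25-40%. The control count rests on the further inference stated above. The simulation uses assumed TBR values; that a positives-only mean does not reflect frequency does not depend on them.

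The presence endpoint, its Chi-squared comparison, the sample size and the non-coronary regions are not affected. This should be fixed before scans are read. It does not undermine the study as a whole.

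**What to change.** Reconcile 6.7 and 9.2 to a single rule:

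- Measure TBR in the same pre-listed coronary regions, for example each major epicardial vessel on the CT coronary angiogram, in every participant and every control scan, whether or not uptake or thrombus is seen.
- Name one value per patient for the case-control comparison of degree, for example the highest coronary TBR, computed identically in controls.
- Report TBR among positive lesions and the proportion positive alongside it.

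The cost is protocol wording, reader time to place regions on negative scans, and re-measurement of the stored control scans. No extra scans or patients are needed. Taking a maximum over regions adds some upward noise, which is why the regions and the summary must be the same in cases and controls.

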## **6.8 Myocardial infarction classification**

Following the completion of all standard of care investigations the participants investigations will be presented to a panel of cardiology experts from the cardiology consultant body at the Royal Infirmary of Edinburgh who will be asked to classify the myocardial subtype using the Universal definition of myocardial infarction (2). This will help to ensure, with addition of the usual care team myocardial infarction classification, a robust classification of the myocardial infarction subtype for each patient.

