cardiovascular conditions (34, 35). We have recently undertaken studies in patients with coronary atherothrombosis in acute type 1 myocardial infarction (35). This was the first demonstration that non-invasive imaging can identify *in vivo* intracoronary thrombus in patients presenting with acute myocardial infarction, and for this work, [name] was awarded the European Society of Cardiology Young Investigator Award in 2021. We have confirmed the high selectivity and specificity of  $^{18}\text{F}$ -GP1 binding to activated platelets within fresh human thrombus and coronary thrombectomy specimens, and importantly we have observed  $^{18}\text{F}$ -GP1 uptake only occurs within the culprit coronary arteries of those with acute myocardial infarction (35). For example, in patients with triple vessel disease, coronary  $^{18}\text{F}$ -GP1 uptake was only seen at the site of the culprit lesion. We have also demonstrated preliminary findings of focal  $^{18}\text{F}$ -GP1 uptake at the site of spontaneous coronary artery dissection, coronary thromboembolism (36) and extra-coronary thrombus including unrecognized left ventricular and atrial thrombus, as well as infarct-related intramyocardial  $^{18}\text{F}$ -GP1 uptake. This changed both the diagnosis (type 1 reclassified as type 2 myocardial infarction) and the treatment (initiation of anticoagulation) of patients presenting with acute myocardial infarction. These data demonstrate the feasibility of identifying patients with intracoronary thrombus and type 1 myocardial infarction, and those with type 2 myocardial infarction caused by spontaneous coronary artery dissection and coronary thromboembolism. Importantly the pattern of  $^{18}\text{F}$ -GP1 distribution differs among these three conditions, allowing their differentiation. This technique holds major promise in aiding the classification of myocardial infarction, especially in patients with myocardial infarction and non-obstructive coronary arteries or where the presence of coronary thrombosis is unclear.

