### *Computed Tomography Positron Emission Tomography*

Imaging datasets will be stored on the servers at the Edinburgh Imaging Facility for subsequent analysis. Summary imaging DICOM files will be uploaded to the PACS system as part of the patient's electronic NHS Lothian medical record.

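### Section 6.8 neither masks the infarct classification to the research PET-CT nor dates the usual-care label, so the subtype used to interpret 18F-GP1 uptake can absorb the scan result

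*Protocol*

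**What the plan says.** Protocol section 6.8 describes the panel step: "Following the completion of all standard of care investigations the participants investigations will be presented to a panel of cardiology experts". It then adds the treating team's label: "This will help to ensure, with addition of the usual care team myocardial infarction classification, a robust classification of the myocardial infarction subtype". The section does not list what the panel sees, does not exclude the research scan, gives no date for the usual-care label, and does not say how disagreement is settled.

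Section 7, under the PET-CT heading, says: "Summary imaging DICOM files will be uploaded to the PACS system as part of the patient's electronic NHS Lothian medical record". No upload time is given.

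Section 6.7 schedules the scan "as soon as practical after their index event and within a maximum of 7 days from symptom onset". The only order the protocol fixes is in section 6.6, where the cardiac MRI precedes the PET-CT.

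Section 1.1.5 says of the earlier 18F-GP1 work: "This changed both the diagnosis (type 1 reclassified as type 2 myocardial infarction) and the treatment (initiation of anticoagulation) of patients".

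No section masks the panel or the treating team to the scan.

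**The concern.** The secondary objective (2.1.2) and part of the secondary endpoints (2.2.2) read 18F-GP1 uptake in the light of the infarct subtype, including thrombosis-related causes of type 2 infarction. That reading is informative only if the subtype was assigned without knowledge of the uptake. If a clinician sees focal uptake and changes the label, the label and the scan agree because one produced the other. This is incorporation bias.

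Two things would be at stake. Agreement between uptake and subtype would look better than it is. Any in-study contrast between what PET shows and what routine evaluation suggests would look smaller than it is. Neither can be repaired at analysis, because a label formed without the scan cannot be recovered once the scan has been seen.

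**Working it through.** **1. Is the route open?** The relevant sections, side by side:

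| Question | Where | What is stated |
|---|---|---|
| What does the panel see? | 6.8 | Participants' investigations, once standard work-up is complete; PET neither listed nor withheld |
| When is the usual-care label fixed? | 6.8 | Not stated |
| Can treating clinicians open the scan? | 7 | Yes: summary images go into the clinical record, time not stated |
| When is the scan done? | 6.7 | Within 7 days of symptom onset |
| What must come before it? | 6.6 | MRI only |
| Has the scan changed labels before? | 1.1.5 | Yes, in earlier patients |

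Nothing forces the label to precede sight of the scan. The schedule in 6.9 puts echocardiography in the same Day 1–7 column as the PET-CT, so standard work-up need not be finished when the scan is done. The route is open. The documents do not show how often it would be used.

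**2. Does the sample size depend on the label?** Inputs from 9.1: routine evaluation 10–20%, incidence to detect 25–40%, power 80–90%, two-sided 0.05, N 36–50. One-sample test of a proportion:

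n = [(z₀.₉₇₅·√(p₀(1−p₀)) + z_power·√(p₁(1−p₁))) / (p₁−p₀)]²

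With p₀ = 0.20 and p₁ = 0.40:
- 80% power: [(1.960 × 0.400 + 0.842 × 0.490)/0.20]², which rounds up to 36.
- 90% power: [(1.960 × 0.400 + 1.282 × 0.490)/0.20]², which rounds up to 50.

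This matches the stated range exactly. The pair 10% against 25% gives 41 and 59, which does not. The range therefore reproduces with routine evaluation entered as a fixed assumed rate. A constant cannot absorb scan results, so the sizing stands whatever happens to the label.

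**3. What if an in-study label were compared with PET?** This is hypothetical: section 9.2 names no such comparison, and the share c of PET-only cases carried into the label is my assumption. Take n = 50, routine positive 10 (20%), PET positive 20 (40%), with every routine positive also PET positive. That leaves 10 discordant patients.

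- c = 0: observed agreement 40/50 = 0.80; expected 0.4×0.2 + 0.6×0.8 = 0.56; kappa = 0.24/0.44 = 0.55; added yield 20 points.
- c = 0.5: label positive 15 (30%); observed 0.90; expected 0.4×0.3 + 0.6×0.7 = 0.54; kappa = 0.36/0.46 = 0.78; added yield 10 points.
- c = 1: agreement 100%; added yield zero.

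If the in-study label rate also replaced the fixed rate in the one-sample test, power at n = 50 would be:

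| c | 20% vs 40% | 10% vs 25% |
|---|---|---|
| 0 | 90% | 86% |
| 0.25 | 67% | 61% |
| 0.5 | 35% | 31% |
| 0.75 | 12% | 11% |

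These figures show the direction and the sensitivity. They are not estimates for this study.

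**The case against.** The best case for the plan has four parts.

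- **The panel file.** Tying the panel to completion of standard-of-care tests can be read as limiting its file to those tests. That reading is reasonable, but the words set a time and do not exclude the scan. It also leaves the usual-care label untouched, and that label is added separately.
- **No reference standard is declared.** The protocol does not call the classification a reference, and 9.2 plans no test of PET against it. The primary endpoint (2.2.1) is the target-to-background ratio, which needs no subtype label. Cohort 2 is recruited by named diagnosis after angiography (4.1, 4.1.2), so that grouping exists at enrolment. All of this stands and narrows the point to interpretation by subtype. The protocol does not say whether the enrolment group or the 6.8 label would define the subtype there.
- **The 10–20% is a prior estimate.** Section 9.1 says "We have estimated that routine clinical evaluation may suggest thrombus in 10-20% of patients". This stands: the stated sample size is unaffected.
- **Limited release of scan information.** Only summary images go to the record, and section 7.1 keeps original reports with the core laboratory. This reduces the exposure but does not close it.

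A reader might infer that the images reach the record within 7 days of onset and that the panel usually meets afterwards. The documents do not support this. The 7-day limit applies to scanning, and neither the upload nor the panel meeting has a date. The defect is that the order is uncontrolled.

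**Conclusion.** The gap is real and limited. As written, 6.8 lets the scan help set the subtype by which 18F-GP1 uptake is then interpreted. This bears on the mechanistic secondary objective, on the type 2 secondary endpoint where it relies on the 6.8 label, and on any in-study comparison with routine evaluation.

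A reader might go further and conclude that the primary endpoint or the sample size is compromised, or that bias has been shown. The documents support none of these. The target-to-background ratio does not use the label, 36–50 reproduces from a fixed rate, and section 1.1.5 describes earlier patients. Contamination is therefore possible, not demonstrated. The kappa, yield and power figures rest on assumed adoption shares and on a comparison the protocol does not state.

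Severity: a cheap improvement, below must-fix. It is worth making before recruitment, because it concerns conduct and a statistical analysis plan cannot restore an unexposed label.

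**What to change.** Amend section 6.8 to say that:

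1. The usual care team's classification is recorded and dated before the PET-CT is performed, for example once the MRI that already precedes it is done.
2. The panel classifies from a file of standard-of-care investigations from which the PET and the research CT coronary angiogram have been removed.
3. This locked classification is used in any analysis of 18F-GP1 by subtype or against routine evaluation.
4. Any PET-informed classification is recorded afterwards as a separate reclassification variable. This keeps the result that section 1.1.5 presents as the promise of the technique.

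The cost is one dated CRF field and the preparation of a masked case file. A usual-care label recorded before the scan may precede some standard tests, such as echocardiography; the masked panel label covers that. No extra patients, procedures or panel members are needed, and release of scan findings for clinical care need not be delayed.
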